#### **3.4 Exclusion Criteria for Arm A and Arm B:**

- 3.4.1 Patients who have had systemic anti-tumor therapy (such as chemotherapy, biologic modifiers or antiangiogenic therapy) within 4 weeks (6 weeks if nitrosourea or mitomycin chemotherapy) prior to study entry.
- 3.4.2 Patients who have had external beam radiation therapy within 1 week or if the adverse events associated with radiation are not resolved to grade 1 or less prior to study entry.
- 3.4.3 Prior therapy with sorafenib (BAY 43-9006), ZD 6474 or AMG-706.
- 3.4.4 Patients currently receiving any other tumor-specific therapy for thyroid cancer or investigational therapy. Patients receiving adjuvant hormonal therapy for a second primary (such as breast cancer or prostate cancer) are allowed to participate as far as there are no known drug interactions.
- 3.4.5 History of allergic reactions attributed to compounds of similar chemical or biologic composition to sorafenib (BAY 43-9006).
- 3.4.6 Patients unable to swallow sorafenib tablets. (e.g. Any condition that impairs patient's ability to swallow pills)
- 3.4.7 Uncontrolled intercurrent illness including, but not limited to, ongoing or active infection, uncontrolled hypertension, or psychiatric illness/social situations that would limit

compliance with study requirements.

- 3.4.8 Patients with any evidence of a bleeding diathesis.
- 3.4.9 Patients actively receiving anticoagulation with therapeutic intent. Prophylactic anticoagulation (i.e. low dose warfarin) or venous or arterial access devices is allowed provided that the PT, INR or PTT are normal.
- 3.4.10 Pregnant women or women who are breast-feeding are excluded from this study because sorafenib (BAY 43-9006) is an investigational agent and teratogenicity has not been evaluated yet. Because there is an unknown but potential risk for adverse events in nursing infants secondary to treatment of the mother with sorafenib (BAY 43-9006), breastfeeding should be discontinued if the mother is treated with sorafenib (BAY 43-9006).
- 3.4.11 HIV-positive patients receiving combination anti-retroviral therapy because of possible pharmacokinetic interactions with sorafenib (BAY 43-9006). Patients with immune deficiency are at increased risk of lethal infections when treated with marrow-suppressive therapy.
- 3.4.12 Patients taking the cytochrome P450 enzyme-inducing antiepileptic drugs (phenytoin, carbamazepine, or Phenobarbital), rifampin or St. John's Wort due to potential drug interactions with sorafenib.

### **3.5 Inclusion of Women and Minorities**

Entry to this study is open to both men and women, and to all racial and ethnic subgroups. Patients will not be excluded from this study on the basis of a history of known HIV positive status.

## **4 TREATMENT PLAN**

### **4.1 Sorafenib (BAY 43-9006) Administration**

Treatment will be administered on an outpatient basis. Reported adverse events and potential risks are described in [Section 6](#). Appropriate dose modifications for sorafenib (BAY 43-9006) are described in [Section 5](#). No investigational or commercial agents or therapies other than those described below may be administered with the intent to treat thyroid cancer.

Sorafenib (BAY 43-9006) will be administered at the dose of 400 mg orally twice a day on a continuous basis. Sorafenib (BAY 43-9006) is supplied as 200-mg tablets. Patients are to swallow the tablets whole with approximately 250 ml (8 oz.) of water, each morning and evening (i.e., approximately 12-hourly). When given with a moderate fat meal, bioavailability was similar to that in the fasted state. With a high fat meal, sorafenib (BAY 43-9006) tosylate's bioavailability was reduced by 29% compared to administration in the fasted state. Thus, it is recommended that sorafenib (BAY 43-9006) be taken on an empty stomach (at least 1 hour before or 2 hours after eating).

Patients will be given monthly calendars (patient diaries) to document the time when the sorafenib (BAY 43-9006) pills are taken. At monthly visits, patients will bring back this record.

Hypertension is a known and potentially serious adverse event associated with Sorafenib (BAY 43-9006) treatment. Patients will have their blood pressure monitored and recorded weekly during the first cycle of therapy, either at the doctor's office or using any calibrated electronic device (such as those found at a local drug store or pharmacy). Patients will be provided with a Blood Pressure Check Diary on which to record the measurements. An increase in blood pressure of > 20 mm Hg (systolic) and 10 mm Hg (diastolic) should be reported to the treating physician immediately. See dose modification guidelines in section 5 in event of drug related hypertension.

Oral or intravenous (IV) bisphosphonates therapy will be allowed for patients with bony metastasis at the investigator's discretion.

Close monitoring is recommended for patients taking BAY 43-9006 tosylate and CYP3A4 inducers. The CYP3A4 inducers such as antiepileptic drugs (phenytoin, carbamazepine, or Phenobarbital), rifampin or St. John's Wort are not permitted on the protocol due to potential drug interactions with sorafenib.

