**In the event of treatment-emergent Hypertension:**

Grade of hypertension Event (CTCAE v.3)	Management/ Next Dose
grade 1	Consider increased BP monitoring
grade 2 asymptomatic and diastolic BP < 110 mm Hg	Begin anti-hypertensive therapy and continue agent
grade 2 symptomatic/ persistent OR diastolic BP ≥ 110 mm Hg OR grade 3	1. Agent should be held* until symptoms resolve and diastolic BP ≤ 100 mm Hg; also treat patient with anti-hypertensives and restart at reduced dose of 600 mg/day given as 400 mg in the AM and 200 mg in the PM. Dose can be re-escalated to full dose as tolerated. 2. If diastolic BP not controlled (≤ 100 mm Hg) on therapy, reduce to another dose level with a dose of 400 mg/day given as 200 mg in the AM and 200 mg in the PM. **
grade 4	Discontinue protocol therapy

\* Patients requiring a delay of > 3 weeks should go off protocol therapy.  
\*\* Patients requiring > 2 dose reductions should go off protocol therapy.

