METABOLISM AND NUTRITION DISORDERS			
Anorexia			Anorexia (Gr 3)
Hyperglycemia	Hypercalcemia		Hyperglycemia (Gr 3)
	Hyperkalemia		Hyperkalemia (Gr 3)
	Hypernatremia		
Hypoalbuminemia			Hypoalbuminemia (Gr 3)

Adverse Events with Possible Relationship to Sorafenib (BAY 43-9006) (CTCAE 4.0 Term) [n= 2571]			Specific Protocol Exceptions to Expedited Reporting (SPEER)
Likely (>20%)	Less Likely (<=20%)	Rare but Serious (<3%)	
Hypocalcemia			Hypocalcemia (Gr 3)
	Hypoglycemia		Hypoglycemia (Gr 2)
	Hypokalemia		Hypokalemia (Gr 3)
Hyponatremia			Hyponatremia (Gr 3)
Hypophosphatemia			Hypophosphatemia (Gr 3)
MUSCULOSKELETAL AND CONNECTIVE TISSUE DISORDERS			
	Arthralgia		Arthralgia (Gr 3)
	Back pain		Back pain (Gr 3)
	Bone pain		
	Musculoskeletal and connective tissue disorder - Other (muscle spasm)		
	Myalgia		
	Pain in extremity		Pain in extremity (Gr 3)
NEOPLASMS BENIGN, MALIGNANT AND UNSPECIFIED (INCL CYSTS AND POLYPS)			
	Treatment related secondary malignancy		
NERVOUS SYSTEM DISORDERS			
	Dizziness		
	Headache		Headache (Gr 3)
		Intracranial hemorrhage	
		Reversible posterior leukoencephalopathy syndrome	
PSYCHIATRIC DISORDERS			
	Insomnia		
RENAL AND URINARY DISORDERS			
	Acute kidney injury		
RESPIRATORY, THORACIC AND MEDIASTINAL DISORDERS			
	Cough		Cough (Gr 2)
	Dyspnea		Dyspnea (Gr 3)
	Respiratory hemorrhage 		

Adverse Events with Possible Relationship to Sorafenib (BAY 43-9006) (CTCAE 4.0 Term) [n= 2571]			Specific Protocol Exceptions to Expedited Reporting (SPEER)
Likely (>20%)	Less Likely (<=20%)	Rare but Serious (<3%)	
	Voice alteration		
SKIN AND SUBCUTANEOUS TISSUE DISORDERS			
Alopecia			Alopecia (Gr 2)
	Dry skin		Dry skin (Gr 2)
Palmar-plantar erythrodysesthesia syndrome		Erythema multiforme	Palmar-plantar erythrodysesthesia syndrome (Gr 3)
	Pruritus		Pruritus (Gr 3)
Rash maculo-papular			Rash maculo-papular (Gr 3)
		Stevens-Johnson syndrome Toxic epidermal necrolysis	
VASCULAR DISORDERS			
	Hypertension		Hypertension (Gr 3)
		Thromboembolic event	

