## 8 STUDY CALENDAR

	Pre-therapy a	Course I (subsequent courses as course I b )		Off-therapy c
		Week 4 b	Week 8	
Sorafenib (BAY 43-9006) d				
Patient diaries		X	X	X
History/Physical Exam	X	X	X	X
Vital signs/Weight	X	X	X	X
Blood pressure monitoring	Once a week till stable or at least for the first 4 weeks.			X
Adverse Event Evaluation		X	X	X
CBC w/diff, platelets	X	X	X	X
Serum chemistry e	X e	X e	X e	X e
Serum β-HCG f	X f			
CT or MRI scan of neck/chest/abdomen g	X g		X g	X g
Serum Calcitonin and CEA	X		X	X
Following tests may be done in selected group of patients ONLY. See Sec7.0 for the details.				
10-mLblood for procurement of serum ( Section 7.1 )	X			
PET scan ( Section 7.2 ) h	X		X	X
DCE-MRI scan ( Section 7.3 )	X		X	X i
20-mLblood for plasma and PBMCs ( Section 7.4 )	X			
FNA biopsy of the tumor ( Section 7.5 )	X k		X k	X j
Paraffin tumor tissue block ( Section 7.6 )	X			
RET genotyping to clinical lab ( Section 7.6 )	X			
a: Pre-therapy evaluations are to be conducted within 10 days prior to administration of sorafenib (BAY 43-9006) except imaging studies, research blood draws, and tumor biopsies that should be done within 4 weeks prior to the start of therapy.				
b: Week 4 evaluations may be done at local doctor's office. However, AE eval must be by research staff via phone interview with the patient and principal investigator must sign off on adverse event data forms within 36 hours of the phone interview.				
c: Off-therapy evaluations are to be conducted within 4 weeks after last dose of sorafenib (BAY 43-9006) treatment. Serum calcitonin and CEA, CT/MRI scans will be optional if a patient received sorafenib (BAY 43-9006) for ≤4 weeks.				
d: Oral sorafenib (BAY 43-9006) will be given with 250 ml (about 8 ounces) of water at the dose of 400 mg BID.				
e: Sodium, Potassium, Chloride, Bicarbonate, Creatinine, BUN, Glucose, Phosphorus, Total protein, Albumin, Total bilirubin, S GOT (AST), SGPT (ALT), Alkaline phosphatase, LDH.				
f: Pregnancy test (sensitivity of at least 50 mIU/mL) will be performed for all women of childbearing potential before beginning sorafenib (BAY 43-9006).				

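### Section 4.1's immediate-report sentence for blood pressure is ambiguous: if both rises are needed, it leaves out a diastolic reading that Section 5 lists in its hold row

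*Combined protocol and SAP*

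**What the plan says.** Section 4.1 describes hypertension as a known and potentially serious effect of sorafenib. It asks for weekly readings during the first cycle, taken "either at the doctor's office or using any calibrated electronic device (such as those found at a local drug store or pharmacy", and entered in a Blood Pressure Check Diary. It then gives the reporting instruction: "An increase in blood pressure of > 20 mm Hg (systolic) and 10 mm Hg (diastolic) should be reported to the treating physician immediately". The next sentence is a pointer: "See dose modification guidelines in section 5 in event of drug related hypertension".

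The Section 5 hypertension table has a row for "grade 2 symptomatic/ persistent OR diastolic BP ≥ 110 mm Hg OR grade 3". Its action begins: "Agent should be held* until symptoms resolve and diastolic BP ≤ 100 mm Hg". The patient is also treated with anti-hypertensives and restarts at a reduced dose.

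The Study Calendar (Section 8) sets monitoring at "Once a week till stable or at least for the first 4 weeks", with vital signs, diaries and adverse-event evaluation at weeks 4 and 8. Its footnote b adds: "Week 4 evaluations may be done at local doctor's office. However, AE eval must be by research staff via phone interview with the patient".

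**The concern.** The instruction in 4.1 joins its two limits with *and* and does not say whether each stands alone. It prints a single greater-than sign, so it is unclear whether that sign also governs the 10 mm Hg. It names no reference reading from which the increase is measured.

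This matters because 4.1 is the only place in the supplied text that says which out-of-clinic readings must reach a physician at once. A reading on a drug-store device may be seen by nobody but the patient. If both rises are needed, a reading that meets the diastolic criterion in the hold row can sit in the diary until a later weekly reading meets the trigger, another contact occurs, or the next scheduled review takes place. A hold that Section 5 calls for could be delayed by that much.

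**Working it through.** The plan states no figure to reproduce. The check applies the 4.1 trigger under each reading and compares the result with the diastolic criterion in Section 5.

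**Inputs.** From 4.1: systolic limit, a rise of more than 20; diastolic limit, a rise of 10. From Section 5: diastolic 110 or more, joined to the other criteria by OR. The documents give no baseline pressures, so those below are assumptions.

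**Rules.** Let ΔS and ΔD be the rises from baseline, and D the diastolic reading.
- One limit per component: report if ΔS > 20 or ΔD > 10.
- Both required: report only if ΔS > 20 and ΔD > 10.
- Section 5 diastolic criterion: D ≥ 110, whatever ΔS is.

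| Assumed change | ΔS | ΔD | One limit each | Both required | D ≥ 110 |
|---|---|---|---|---|---|
| 130/85 to 148/112 | 148 − 130 = 18 | 112 − 85 = 27 | report (27 > 10) | no (18 is not > 20) | yes |
| 140/100 to 155/110 | 155 − 140 = 15 | 110 − 100 = 10 | no | no | yes |

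**First row.** The two readings of the sentence give opposite answers. If both rises are needed, the same gap appears at any baseline whenever diastolic reaches 110 or more and systolic rises by 20 or less.

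**Second row.** A gap remains on either reading. Diastolic reaches 110 with a rise of 110 − D₀, where D₀ is the baseline. The diastolic limit is missed when 110 − D₀ ≤ 10, that is D₀ ≥ 100. If a rise of exactly 10 were meant to count, it is missed when D₀ > 100. Either way the gap starts at a baseline of about 100, provided systolic also rises by 20 or less.

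**Does another section settle it?**
- The pointer in 4.1 leads to a table that says what to do once a reading is known. It does not require anyone to pass a reading on.
- Section 10.1 covers reports from investigators to CTEP, not from patients to physicians.
- The calendar provides scheduled review, not immediate reporting.
- Within the Section 5 table, *and* joins conditions that must both hold and OR marks alternatives. A reader who carries that usage back to 4.1 would require both rises.

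**The case against.** The strongest reply is that one limit per component is the more natural reading. Each number carries its own label, which is ordinary shorthand, and on that reading 148/112 is reportable at once. This stands, and it is why the point is one of ambiguity. A reader might infer that the protocol actually requires both rises; the sentence does not say so.

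The two rules also have different jobs: 4.1 is an early warning based on change, while Section 5 gives management levels. The first need not copy the second, and nothing tells patients or staff to disregard other readings. That is fair, but an early warning should at least cover a level at which the drug is to be held.

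The Section 5 column is headed by grade of event, so the 110 limit may be meant to separate grade 2 events rather than classify one drug-store reading. Treating a single reading as meeting it takes the printed OR at face value, which is an assumption.

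Finally, what patients were told cannot be checked. The diary is not in the supplied text and consent pages were removed from it.

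A reader might also infer a delay of several weeks, a count of doses taken in the meantime, or a number of patients affected. The documents support none of these. A long delay needs every intervening weekly reading and every other contact to miss the problem. The CAEPR band for hypertension (up to 20%) covers any grade. Applied to the sample size, it would give an expected count rather than a cap, and it says nothing about the subset at issue here.

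**Conclusion.** The ambiguity is real and minor. If both rises are required, an out-of-clinic diastolic reading of 110 mm Hg or more with a systolic rise of 20 or less escapes the immediate-report instruction, although Section 5 lists that diastolic level in its hold row. On either reading a small gap remains for patients with a baseline diastolic of about 100 or more. That should be uncommon, because 3.4.7 excludes uncontrolled hypertension.

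The conclusion rests on taking the OR in Section 5 as printed, on illustrative baselines, and on the supplied text alone. It applies only to readings taken outside the clinic, since staff see the others. Its frequency and any resulting delay cannot be estimated from the documents. The Section 5 hold rule, the response endpoint, the two-stage sample size and the analysis are unaffected.

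**What to change.** Replace the sentence in 4.1 with wording to this effect: *Report to the treating physician at once any rise from the pre-therapy reading of more than 20 mm Hg systolic OR more than 10 mm Hg diastolic, and any diastolic reading of 110 mm Hg or higher.*

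Changing *and* to *or* is the main correction: the first example is then caught, since 27 > 10. The absolute limit closes the remaining gap: the second example is caught because its diastolic reading is 110. Naming the pre-therapy reading and stating the inequality for both components removes the other two uncertainties. Check the Blood Pressure Check Diary and align it if it repeats the present wording.

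The cost is a one-sentence amendment, possibly a reprinted diary card, and some extra patient calls for a rise in one component only.

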#### **4.2 Supportive Care Guidelines**

Prophylactic use of anti-emetics, anti-diarrheal treatment, or growth factors is not recommended. However, anti-emetics, anti-diarrheal treatment or growth factors may be used for acute treatment of toxicities and growth factors may be offered as per the ASCO guidelines.

For patients who develop hand-foot reaction, treatment with topical emollients (such as *Aquaphor*) for symptom relief is recommended. Topical and/or oral steroids or anti-histamine agents may be used. High dose vitamin B6 (pyridoxine; up to 400 mg orally each day) may also be used.

#### **4.3 Duration of Therapy**

In the absence of treatment delays due to adverse event(s), treatment will continue until one of the following criteria applies:

- Progressive Disease and no clinical benefit (Note: patients who have continued clinical benefit such as symptomatic or tumor marker improvement or decreased tumor burden compared to baseline or limited progression in non-target lesion treated with radiation or surgery will be able to continue therapy)
- Completion of 8 weeks of therapy after complete remission
- Off of study drug due to any reason for more than 21 consecutive days
- Intercurrent illness that prevents further administration of treatment
- Unacceptable adverse event(s)
- Patient decides to withdraw from the study
- General or specific changes in the patient's condition render the patient unacceptable for further treatment in the judgment of the investigator.

## 5 DOSING DELAYS/DOSE MODIFICATIONS

- For delay of treatment due to toxicity for more than 21 days, patient will be removed from the study.

**Dose should be modified and/or delayed according to the following guidelines:**

**In the event of grade 3 or 4 drug-related non-hematologic toxicity**, therapy will be held till the toxicity has resolved to baseline or  $\leq$  grade 1. For delay of treatment due to toxicity for more than 21 consecutive days, patient will be removed from the study. Once toxicity is resolved to baseline or  $\leq$  grade 1, sorafenib (BAY 43-9006) should be started at a reduced dose of 200 mg PO BID. If tolerated, the dose can be re-escalated to 600 mg/day given as 400 mg in the AM and 200 mg in the PM. If 600 mg/day dose is tolerated, further re-escalation to the full dose of 400 mg PO BID may be done after discussing with protocol chair.

**In the event of grade 2 hand-foot skin reaction or recurrent grade 2 drug-related non-hematologic toxicity**, therapy may be held till the toxicity has resolved to baseline or  $\leq$  grade 1. For delay of treatment due to toxicity for more than 21 consecutive days, patient will be removed from the study. Once toxicity is resolved to baseline or  $\leq$  grade 1, sorafenib (BAY 43-9006) should be started at a reduced dose of 200 mg PO BID. If tolerated, the dose can be re-escalated to 600 mg/day given as 400 mg in the AM and 200 mg in the PM. If 600 mg/day dose is tolerated, further re-escalation to the full dose of 400 mg PO BID may be done after discussing with protocol chair.

**In the event of GI-Perforation**, patient will be removed from the study and followed until adverse event is resolve.

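### Section 5 directs a restart at 200 mg BID after most resolved grade 3 or 4 non-hematologic toxicities, with no bar on rechallenge after events such as anaphylaxis and no rule for recurrence at that dose

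*Combined protocol and SAP*

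**What the plan says.** Section 5 (Dosing Delays/Dose Modifications) treats the two highest non-fatal grades under one rule: "In the event of grade 3 or 4 drug-related non-hematologic toxicity", therapy is held until the event is back to baseline or to grade 1 at most. A delay of more than 21 consecutive days removes the patient. Otherwise sorafenib "should be started at a reduced dose of 200 mg PO BID". If that is tolerated, the dose may rise to 600 mg/day, and "further re-escalation to the full dose of 400 mg PO BID may be done after discussing with protocol chair".

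Two events have their own rules in Section 5:

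- **GI perforation:** "patient will be removed from the study and followed until adverse event is resolve".
- **Hypertension:** a separate table. Grade 4 reads "Discontinue protocol therapy". Grade 3, and the more serious forms of grade 2, restart at 600 mg/day. Its footnotes end therapy for a delay of more than 3 weeks and add that "Patients requiring > 2 dose reductions should go off protocol therapy".

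Section 4.3 (Duration of Therapy) separately ends treatment for more than 21 consecutive days off drug, for an adverse event that is unacceptable (a term it does not define), and for changes that "render the patient unacceptable for further treatment in the judgment of the investigator".

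**The concern.** The restart wording is an affirmative direction that covers any drug-related non-hematologic event of grade 3 or 4 that resolves in time. The protocol's own risk list (Section 6.2) names anaphylaxis, Stevens-Johnson syndrome and toxic epidermal necrolysis as rare but serious events possibly related to sorafenib. If one of these occurs and resolves within 21 days, the literal text of Section 5 points to giving the drug again.

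The plan is also uneven. Exclusion 3.4.5 keeps out a patient with a past allergic reaction to a similar compound, yet Section 5 has no bar for a patient who has just had anaphylaxis on sorafenib itself. Grade 4 blood pressure ends therapy outright, while other grade 4 non-hematologic events share the grade 3 restart rule.

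The second gap concerns a patient already on 200 mg BID who has another grade 3 or 4 event. Section 5 names no lower dose, no stop and no limit on repeats for this case. At stake is avoidable harm to a patient at a site that follows the text as written.

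**Working it through.** No stated statistical figure bears on this point, so the check sets the sections side by side and follows the dose path.

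**1. Exits from the general rule.** Within the grade 3 or 4 paragraph of Section 5, the only route off study is a delay of more than 21 consecutive days. An event that resolves by day 21 does not meet it. Neither grade 4 as such nor recurrence is an exit.

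**2. Dose change on restart.** The only restart dose named in that paragraph is 2 × 200 = 400 mg/day.

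| Dose at the event | Restart dose | Change |
|---|---|---|
| 800 mg/day | 400 mg/day | 400 − 800 = −400 mg/day |
| 600 mg/day | 400 mg/day | 400 − 600 = −200 mg/day |
| 400 mg/day | 400 mg/day | 400 − 400 = 0 mg/day |

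The last row is an inference. The text speaks of a reduced dose and does not address a patient already at 200 mg BID. What the documents do show is that no rule fits that patient.

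**3. Where the protocol chair enters.** After a hold the path has three steps: 400, then 600, then 800 mg/day. Chair discussion is required at one of the three, the last. The restart itself, including after a grade 4 event, needs none.

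**4. The limit on dose reductions.** This footnote is keyed to a row of the hypertension table. Even if it is read as general, it counts reductions, so a restart at an unchanged 200 mg BID would not use one up.

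**5. Section 4.3 against Section 5.** Section 4.3 can end treatment for the events at issue. However, its lead-in is framed for the case without treatment delays from adverse events, its key term is undefined, and neither section ranks the two. For GI perforation and grade 4 hypertension, the authors wrote explicit stops as well.

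**6. Oversight before a restart.** A hold may end on any day up to day 21. Disease Group review (Section 10.1.4) is at least monthly; taking that as an interval of up to about 30 days (an assumption), 21 < 30, so a restart can precede it. Expedited reporting (Section 10.1.1) is faster. Related grade 4 events are reported within 24 hours if unexpected and within 10 calendar days if expected, and Section 10.3 passes the reports to the chair. None of these provisions makes restart wait for the review.

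**The case against.** The strongest reply is that Section 4.3 decides whether treatment continues, and Section 5 sets the dose only if it does. Section 4.3 itself lists more than 21 days off drug, so it plainly covers toxicity holds despite its lead-in. Section 5 calls its rules guidelines and words the restart as a recommendation, and exclusion 3.4.5 shows the authors' attitude to allergy. A prudent investigator would probably not rechallenge after anaphylaxis. All of this stands as a reason to expect good practice. It does not supply a rule, because the decision turns on an undefined term with no stated precedence.

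Several stronger readings are tempting but not supported:

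- *The protocol has no mandatory stop for these patients.* It has the 21-day limit, and Section 4.3 ends treatment once an event is judged unacceptable.
- *GI perforation and grade 4 hypertension are the only stops in Section 5.* The hypertension table also stops for delay and for the number of reductions.
- *Section 5 instructs a same-dose restart at 200 mg BID.* That follows only from literal application; the text is silent.
- *Restart would follow myocardial infarction, intracranial hemorrhage or hepatic failure.* The documents do not show that these could reach grade 1 within 21 days. The grading definitions (CTCAE version 3.0) are not reproduced.
- *The number of listed serious events without a named stop measures the risk.* It counts table entries, not patients.

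It is also fair to object that a blanket stop for any recurrent grade 3 event would be too broad. Section 6.2 lists laboratory abnormalities such as raised lipase and low phosphate as likely (>20%). A responding patient should not lose therapy automatically for a manageable one.

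**Conclusion.** The concern holds for grade 3 or 4 drug-related non-hematologic toxicity other than hypertension and GI perforation. Section 5 directs restart at 200 mg BID after timely resolution, without a separate grade 4 rule, a bar on rechallenge after events such as anaphylaxis, or any provision for recurrence at that dose. Section 4.3 is a real but discretionary backstop.

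The number of patients affected cannot be computed from the documents and is likely small. Section 2.5 reports 0% skin toxicity above grade 3 at an initial dose of 400 mg BID, but that figure says nothing about anaphylaxis or other non-skin events. The case for change rests on the severity of a foreseeable event and the low cost of the wording, not on frequency. It assumes that a site may follow Section 5 as written, and that an event of the kind named can resolve within the hold. The response analysis is not in question: under Section 11.4.2, eligible patients who stop early stay in the main analysis.

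**What to change.** Amend Section 5 in four places:

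1. State that the stopping criteria of Section 4.3 take precedence over the restart rules.
2. Extend the GI-perforation line, with no restart, at least to drug-related anaphylaxis, Stevens-Johnson syndrome and toxic epidermal necrolysis. Whether to add others, such as myocardial infarction or intracranial hemorrhage, is for the sponsor's clinical judgment.
3. Require discussion with the protocol chair before restart after any other grade 4 drug-related non-hematologic toxicity.
4. For grade 3 or 4 toxicity recurring at 200 mg BID, end protocol therapy unless the chair agrees to continue, for example for a manageable asymptomatic laboratory abnormality.

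The grade 3 hold and first restart, the grade 2 rule and the hypertension table stay as they are. Repeated cycles between 400 and 600 mg/day would remain uncapped, but each of those restarts is a true reduction.

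The cost is a few chair discussions, with no added patients, visits or procedures. The downside is that a few patients may leave therapy earlier, in a disease for which Section 2.6 says there is no standard systemic treatment. The chair's discretion in items 3 and 4 is there to limit that loss.
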